12.2.2 Secondary Estimand – Per-Protocol (PP) Analysis

This estimand aims to measure the effect of cilostazol only in patients who completed the treatment without interruption.

- Target Population: Patients who received at least 80% of prescribed doses over the 14-day treatment period.
- Variable of Interest: mRS at 6 months (favorable vs. unfavorable) otherwise LOCF.
- Handling of Intercurrent Events:
 - Early treatment discontinuation → "Principal Stratum" strategy: Only patients who completed treatment are analyzed.
 - Death before 6 months → "Composite" strategy (mRS=6 if neurological, secondary analysis excluding non-neurological deaths).
- Estimation Method: Logistic regression model restricted to patients who completed treatment.

◆ Justification: This analysis assesses the specific effect of cilostazol without treatment adherence interference.

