12 STATISTICAL ASPECTS

12.1 Description of statistical methods to be used including the timetable for the planned interim analyses

CASH is a multicentre, double-blinded, randomised, placebo-controlled, parallel-group superiority trial in adult, using an adaptive group-sequential design, to demonstrate that cilostazol plus nimodipine is safe and superior to nimodipine alone will improve modified Ranking Score (mRS) at six months.

Two interim analyses for futility and efficacy are planned.

Populations

For the statistical analysis, the following populations are defined:

Population	Description
Intent-To-Treat (ITT) Population	The ITT population will include all randomised participants. ITT participants will be analysed according to the randomised treatment, regardless of the actual treatment received. All efficacy analyses will be performed on the ITT population.
Per Protocol (PP) Population	The PP population will include all participants in the ITT with at least 80% of doses received to define adherence to treatment. The PP population will be used for supportive analyses of efficacy measures.
Safety Population (SP)	The SP will include all randomised participants who received at least one treatment (active or placebo). The SP will be analysed according to the actual treatment received. This population will be used for safety analyses.

Description of the statistical methods, including the timing of planned interim analyses

The statistical analysis plan (SAP) will be developed and finalised before the database is locked.

Below is a description of the planned statistical analysis. Further details will be presented in the statistical analysis plan (SAP).

All statistical analyses will be performed with SPSS version 26 or RStudio. For analyses performed with RStudio, the script used will be provided.

The baseline is defined as the last evaluation performed before the start of the study treatment, day 1 (V1).

All data collected after the start of the study treatment are defined as post-baseline.

Baseline characteristics will be summarised by the treatment group. The mean and standard deviation (SD) or median and interquartile range (IQR) for skewed variables will be summarised for continuous measures.

The proportion in each category will describe categorical variables.

In addition, the 95% confidence interval (CI) will also be calculated as indicated.

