12.2 Definition of Estimands in the CASH Trial

We define two primary estimands corresponding to the intention-to-treat (ITT) and per-protocol (PP) analyses, as well as an additional estimand incorporating neurological mortality.

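### The supportive per-protocol estimand is labelled a principal stratum but analyses observed completers, and its completion rule removes early neurological deaths that the same section scores as mRS 6

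*Protocol*

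**What the plan says.** Section 12.2.2 gives the aim first: "This estimand aims to measure the effect of cilostazol only in patients who completed the treatment without interruption". Its target population is worded differently: "Patients who received at least 80% of prescribed doses over the 14-day treatment period". For early discontinuation it names a principal-stratum strategy, explained as "Only patients who completed treatment are analyzed". The estimator is "Logistic regression model restricted to patients who completed treatment". Death before 6 months falls under a composite "strategy (mRS=6 if neurological, secondary analysis excluding non-neurological deaths".

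The table in section 12.3 repeats both rules for the per-protocol column. Early discontinuation leads to exclusion; neurological death counts as mRS 6, on the ground that this keeps the groups comparable.

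Section 12.1 defines the analysis set by adherence, "The PP population will include all participants in the ITT with at least 80% of doses received to define adherence to treatment", and gives it a limited role: "The PP population will be used for supportive analyses of efficacy measures". Section 12.2, however, opens with "We define two primary estimands corresponding to the intention-to-treat (ITT) and per-protocol (PP) analyses", while the heading of 12.2.2 calls the per-protocol estimand secondary.

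Two other places decide who can complete. Section 7.1.1 sets the course at two tablets a day for 14 days, 28 in total. Section 5.8.1.1 stops treatment when a patient leaves the ICU during the administration period.

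**The concern.** A principal stratum is defined by what a patient would do under both assignments, for example patients who would complete treatment whether given cilostazol or placebo. Section 12.2.2 instead takes those who did complete in the arm they were given, and states no assumption or method that would link this group to a stratum. If treatment affects who completes, the two groups of completers are not comparable, and the label gives the result a causal reading that it does not have.

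Such an effect is plausible on the protocol's own account. Section 2.2 places most delayed cerebral ischaemia between days 4 and 10, inside the dosing period, so a drug that prevents it could change who survives and completes. Section 4.1.2 lists arrhythmia, bleeding and allergy as major cilostazol-related events, although section 12.3 expects no intercurrent event directly related to the drug.

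The death rule makes this concrete. Death during dosing ends treatment, so the exclusion rule and the composite rule meet in the same patient. If exclusion wins, the worst outcomes leave the analysis, possibly in different proportions by arm. At stake is how far the supportive analysis can be trusted when it is set beside the main result.

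**Working it through.** **Figures in the plan.** No stated figure rests on the per-protocol set. The sample size in section 12.5 (284 per arm, stated power 0.8016) takes no input from it. Simulating the three looks with the section 12.5 boundaries returns a power of 0.80, so the design reproduces.

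**Step 1: who can qualify.** 80% of 28 tablets is 0.80 × 28 = 22.4, so 23 are needed. At two a day, 23 / 2 = 11.5 days. A patient who dies before about day 11.5 of treatment cannot reach the threshold. Neurological deaths after that point can still be kept as mRS 6.

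**Step 2: the two readings of the denominator.**

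- Doses counted over the full 14 days: an early death fails the 80% rule and is dropped, so the composite rule cannot reach it.
- Doses counted only up to death: the patient may meet the 80% rule but has not completed treatment, and both the exclusion rule and the model are restricted to completers.

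The passages conflict under either reading.

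**Step 3: what exclusion can do.** The documents do not give the share of deaths before about day 11.5, so the shares below are assumptions. Let 65% of all randomised patients have a favourable outcome in each arm. The 65% is the control rate in section 12.5; setting both arms equal represents no effect. Let d be the share who die early and are excluded; all are unfavourable.

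- Favourable rate among completers = 0.65 / (1 − d)
- Odds among completers = 0.65 / (0.35 − d)
- Odds ratio, cilostazol to control = (0.35 − d_control) / (0.35 − d_cilostazol)

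| Early deaths, control / cilostazol | Favourable among completers | Odds ratio | Chance of a one-sided 0.025 result favouring cilostazol |
|---|---|---|---|
| 5% / 5% | 68.4% / 68.4% | 0.30/0.30 = 1.00 | 2.5% |
| 5% / 8% | 68.4% / 70.7% | 0.30/0.27 = 1.11 | 8% |
| 5% / 10% | 68.4% / 72.2% | 0.30/0.25 = 1.20 | 16% |
| 10% / 5% | 72.2% / 68.4% | 0.25/0.30 = 0.83 | 0.2% |

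The last column comes from 400,000 simulated trials with 284 randomised per arm and an unadjusted two-proportion Z-test in completers.

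**Step 4: equal shares are neutral only without an effect.** At the planned 65% and 76%, the odds ratio among all randomised is (0.76/0.24) / (0.65/0.35) = 1.71. Excluding 10% early deaths from each arm gives (0.76/0.14) / (0.65/0.25) = 2.09.

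**Step 5: a second selection.** Stopping at ICU discharge can exclude early-discharged patients as well. If a share g of favourable patients is lost this way, the Step 3 odds ratio is multiplied by (0.65 − g_cilostazol) / (0.65 − g_control). This factor can be above or below 1, so it may add to the effect of excluding deaths or offset it.

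**The case against.** The strongest reply is that nothing confirmatory depends on this analysis. Section 12.1 runs the primary analysis on the intention-to-treat population, lists the per-protocol repeat among the sensitivity analyses and calls it supportive. The headings of 12.2.1 and 12.2.2 rank the estimands as primary and secondary. This stands. A reader might infer from the opening of 12.2 that the per-protocol result shares in the trial's decision. The rest of section 12 does not support that, and the phrase is best treated as a slip to correct.

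Second, removal of early deaths is not stated outright. Discontinuation and death are listed as separate intercurrent events, and an adherence denominator is often settled in the SAP. This stands in part: the exclusion follows from applying the text literally. But the protocol itself fixes completion, the 80% rule and the death rule, and Step 2 shows that they collide whichever denominator is chosen.

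Third, a reader might infer that the analysis would show a benefit where there is none. That needs more early deaths on cilostazol. The trial's own hypothesis points to fewer, and the bias would then run against the drug. The no-effect scenarios with unequal shares also require an exact offset among patients who survive the early period, so that the overall favourable rates stay equal. Section 12.5 notes that patients with early death and without surgery are not included, which should keep the shares low. These limits all stand.

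Fourth, a reader might take 12.2.2 to score every death as mRS 6. It says so for neurological deaths only, and later neurological deaths are kept.

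Finally, any per-protocol analysis drops patients who stop for adverse events. That is true, and such an analysis is acceptable if described as what it is; here it carries a principal-stratum label.

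**Conclusion.** The point holds as a defect in a supportive analysis. Three parts follow from the text alone: observed completers are not a principal stratum; the completion rule and the death rule conflict for neurological deaths before about day 11.5, with no precedence stated; and the adherence rule and the rank of the estimand are each worded in two incompatible ways.

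The size and direction of any bias are not fixed by the documents. Over the assumed early-death shares with no effect, the completer odds ratio runs from 0.83 to 1.20 and stays at 1.00 when the shares are equal. The stop at ICU discharge makes the net direction unknown. The intention-to-treat estimand, sample size, stopping boundaries and alpha are not affected. The correction should be made before unblinding.

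**What to change.** - Measure adherence against doses due while the patient is alive and within the treatment window. Keep patients who were adherent until death in the per-protocol set, with neurological deaths as mRS 6 and non-neurological deaths handled as in the intention-to-treat estimand.
- State how a stop at ICU discharge counts towards adherence.
- Use the 80% rule throughout, in place of completion without interruption.
- Drop the principal-stratum label in 12.2.2 and 12.3, and describe the result as a supportive per-protocol analysis open to selection bias.
- Reword the opening of 12.2 so that intention-to-treat is the only primary estimand.

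The cost is protocol and SAP wording plus minor programming; no new data and no change in sample size. The per-protocol set becomes slightly larger. Some selection on adherence after randomisation remains, which is why the change of label is needed as well as the change of denominator.

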12.2.3 Additional Estimand – Impact of Mortality on the Analysis

An additional estimand will be conducted to specifically evaluate the impact of neurological vs. non-neurological mortality:

- Target Population: All randomized patients.
- Variable of Interest: mRS at 6 months, considering:
 - mRS=6 for neurological deaths.
 - Exclusion of non-neurological deaths in a secondary analysis.

◆ Justification: This analysis differentiates the specific effects of treatment on neurological mortality, which is crucial for interpreting the trial results.

12.3 Management of Intercurrent Events – Methodological Approach

In this trial, we do not anticipate the use of rescue therapy, nor the occurrence of an intercurrent event directly related to the drug. The selected strategies reflect this specificity.

Intercurrent Event	Strategy for ITT Estimand	Strategy for PP Estimand	Justification
Early treatment discontinuation	"Treatment Policy" – Analyze in randomized group	"Principal Stratum" – Exclude	Maintains comparability in ITT, assesses adherence in PP.
Neurological death	"Composite" – Counted as mRS=6	"Composite" – Counted as mRS=6	Maintains comparability between groups.
Non-neurological death	"Composite" Sensitivity analysis	"Composite" Sensitivity analysis	Excludes deaths unrelated to the study in a secondary analysis.
Loss to follow-up before 6 months	"Composite" – LOCF + Multiple Imputation	"Composite" – LOCF + Multiple Imputation	Reduces bias due to missing data.

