The incidence rate of SAH is high, 10 per 100.000 among which 85% are caused by a ruptured aneurysm: neurological deterioration is frequent during the ICU stay and is mainly due to delayed cerebral ischemia. The most recent meta-analysis showed that cilostazol significantly reduced poor outcome patients with SAH, with an Odds ratio of 0.52 [0.37 – 0.74] for unfavourable outcome¹⁶. Our trial aims to confirm that a 14 days administration of 100 mg twice a day of cilostazol will reduce by 30% long-term disability and cognitive impairment of aneurysmal SAH. If so, our trial might dramatically change the therapeutic management of aneurysmal SAH, as nimodipine did long time ago. Collective benefit is also expected, including the reduction of the length of hospital stay and need for rehabilitation.

The study protocol will not interfere with other preventive or curative treatment of DCI and vasospasm, which will be kept to the discretion of the physician in charge.

Major secondary effects of cilostazol are arrhythmia, abnormal bleeding, and allergy (frequency not reported). Most frequent adverse reactions are headache (up to 34%), palpitation (up to 10%), and diarrhoea (up to 19%). These side effects are however reported in patients taking cilostazol as a long-term therapy. In previous trial on DCI prevention in SAH, 14 days administration of cilostazol appeared safe since no difference in major adverse events rate was observed between cilostazol and control groups.

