On angiograms in DSA or MR/CTA, the severity of vasospasm will be considered none or mild if there is a less 33% decrease in arterial diameter on angiography, moderate if there is a 34% to 66% decrease, or severe if there is at least a 67% decrease.

DSA or MR/CTA will be performed when:

- There are signs of delayed cerebral ischemia as described above.
- There is a severe impairment of cerebral blood flow velocity assessed with help of transcranial doppler (tCD), as defined below. tCD will be performed at the discretion of the physicians in charge. tCD is a non-invasive radiation free exam that can be used at bedside. Its repetition allows a better detection of vasospasm and is routinely performed. Cerebral vasospasm severity will be evaluated according to this scale:

Degree of cerebral blood velocity alteration	Mean flow velocity (cm/s)	Lindegaard ratio
Mild	120-149	3-6
Moderate	150-199	3-6
Severe	>200	>6

11. Occurrence of new cerebral infarcts

New cerebral infarct is considered when detected on the CT scan or MRI performed with 6 weeks, (or on the latest CT scan or MRI performed before death within 6 weeks, or at autopsy), but not present on the earlier CT or MRI scan performed between 24 and 48 h after early aneurysm occlusion and not ascribable to other causes such as surgical clipping or endovascular treatment. Hypodensities on CT imaging resulting from ventricular catheter or intraparenchymal hematoma should not be considered cerebral infarctions secondary to DCI.

12. Occurrence of cilostazol-related major adverse events, including: arrhythmia, abnormal bleeding and allergy.
13. Occurrence of cilostazol-related minor adverse events include: tachycardia, fever, fainting, nausea, vomiting and stomach pain.

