10.3.3.2 Serious adverse events that require the investigator to immediately notify the sponsor

The investigator must report all adverse events that meet one of the seriousness criteria below, except for events listed in section 10.3.3.1 as not requiring notification:

- 1- Death
- 2- Life threatening situation
- 3- Requiring hospitalisation or prolonging hospitalisation
- 4- Persistent or significant disability or incapacity
- 5- Congenital abnormality or birth defect
- 6- Or any other adverse event considered "medically significant"

- ❖ For serious adverse events related to the experimental medication(s) and which are expected:
 - the -SmPC for the « **cilostazol** » speciality, found in (Appendix 5), should be consulted.
- ❖ The serious adverse events associated with specific research procedures or exams, and which are expected, are:
 - Poorly tolerated auricular or ventricular arrhythmia
 - Abnormal bleeding (requiring blood transfusion or not)
 - Allergy

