12.2.1 Primary Estimand – Intention-to-Treat (ITT) Analysis

This estimand aims to assess the effect of cilostazol added to nimodipine on the modified Rankin Scale (mRS) at 6 months, considering all randomized patients, regardless of intercurrent events.

- Target Population: All randomized patients.
- Variable of Interest: mRS at 6 months, dichotomized as favorable outcome (mRS 0-2) vs. unfavorable outcome (mRS 3-6).
- Handling of Intercurrent Events:
 - Early treatment discontinuation → "Treatment Policy" strategy: Patients remain in their randomized group, regardless of treatment adherence.
 - Death before 6 months → "Composite" strategy:
 - Neurological death → Counted as mRS=6.
 - Non-neurological death → Counted as mRS in ITT analysis and a secondary analysis excluding these patients.
 - Loss to follow-up → "Composite" strategy: Last observation carried forward (LOCF) with multiple imputation as a sensitivity analysis.
- Estimation Method: Logistic regression adjusted for age and initial severity (GCS grade) and centre.

◆ Justification: This approach respects the ITT principle, ensures comparability between groups, and provides a realistic assessment of treatment effect.

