12.4 Statistical Analysis and Sensitivity Tests

To ensure robust conclusions, we will apply multiple sensitivity analyses, in addition to ITT and PP analyses:

1. Complete Case Analysis (excluding patients with missing data).
2. Multiple Imputation of missing data to assess the impact of lost-to-follow-up cases.
3. Scenario analysis excluding non-neurological deaths.

Safety analysis

For each patient and each type of toxicity described according to the CTCAE (V.5.0), the worst-case category identified during treatment will be used for the descriptive analysis.

Safety Measures

Safety will be assessed using:

- Incidence of treatment-related adverse events (TEAEs)
- Incidence and severity of treatment-emergent adverse events (TEAEs)
- Incidence of serious adverse events (SAEs)
- Incidence of TEAEs and SAEs leading to discontinuation of study medication.
- Changes in blood chemistry, hematology and coagulation parameter results
- Changes in vital signs including temperature, pulse, respiratory rate, systolic and diastolic blood pressure
- Changes in physical examination results
- Changes in electrocardiogram (ECG) results

These data will be described using lists and tables.

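### The secondary and sensitivity analyses that drop non-neurological deaths can remove deaths caused by cilostazol, and the estimands give those deaths no mRS value

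*Protocol*

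**What the plan says.** Section 12.3 sets out the handling of intercurrent events. Its opening text says the trial does not anticipate rescue therapy, "nor the occurrence of an intercurrent event directly related to the drug", and that the chosen strategies follow from this. In the table below it, neurological death is counted as mRS 6. Non-neurological death gets only a composite label and a sensitivity analysis, justified by "Excludes deaths unrelated to the study in a secondary analysis".

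The same exclusion appears in four other places:

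- Section 12.2.1 (ITT estimand): "Counted as mRS in ITT analysis and a secondary analysis excluding these patients". The mRS value is missing.
- Section 12.2.2 (PP estimand): mRS 6 if the death is neurological, with a secondary analysis that leaves out the others.
- Section 12.2.3 (additional estimand): "Exclusion of non-neurological deaths in a secondary analysis".
- Section 12.4, item 3 of the sensitivity analyses: "Scenario analysis excluding non-neurological deaths".

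The protocol's safety text names the drug's harms. Section 2.7 lists arrhythmia, bleeding and allergy as the major effects and gives no frequency. Section 4.1.2 makes them a secondary endpoint: "Occurrence of cilostazol-related major adverse events, including: arrhythmia, abnormal bleeding and allergy". Section 10.3.3.2 includes "Poorly tolerated auricular or ventricular arrhythmia" among expected serious events, together with bleeding and allergy.

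**The concern.** The protocol treats non-neurological as if it meant unrelated to treatment. For this drug that does not follow. A fatal arrhythmia, extracranial haemorrhage or anaphylaxis is non-neurological, and it is also the kind of death cilostazol could plausibly cause. Removing patients because of a post-randomisation event that treatment can influence means the remaining groups are no longer the randomised groups.

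The trial sets out to show that cilostazol is both safe and superior (section 4.2.1), and section 12.4 offers the exclusion as one of the analyses that make the conclusions robust. A check that can delete toxic deaths may agree with a favourable primary result for the wrong reason, or soften an unfavourable one.

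The missing score adds to this. The ITT estimand gives no number for a non-neurological death. The PP estimand, which the introduction to 12.2 counts among two primary estimands although its own heading calls it secondary, gives no main-analysis value at all.

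**Working it through.** **Step 1. The passages side by side.** Section 12.3 rests on two premises: non-neurological deaths have nothing to do with the study, and no drug-related intercurrent event is anticipated. Sections 2.7, 4.1.2 and 10.3.3.2 name three drug harms whose fatal forms are mostly non-neurological. The first premise is therefore unsupported, and the second is in tension with the safety sections. Nothing cited here defines neurological death. Section 9.3 limits the adjudication committee to secondary endpoints and does not mention cause of death.

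**Step 2. Design inputs.** The plan gives no figure for this point, and the point disputes none. From section 12.5: 65% favourable on control, 76% on cilostazol, 284 per arm, 315 per arm after dropout. As a check that these are the design rates: 284 / (0.65 × 0.35 + 0.76 × 0.24) = 284 / 0.4099 = 692.85, which matches the stated maximum information.

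**Step 3. Effect of exclusion.** Assumptions: no effect of cilostazol other than a fraction d of its arm dying of a drug-caused non-neurological event, with d from 1% to 5%. The documents give no rate. Odds ratios (OR) are for favourable outcome and unadjusted. The placebo odds are 0.65 / 0.35 = 1.857.

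*Case A: deaths strike regardless of prognosis.*
- All deaths counted: favourable rate 0.65(1 − d). At d = 5%: 0.6175 / 0.3825 = 1.614, and 1.614 / 1.857 = 0.87.
- Deaths excluded: 0.65(1 − d) / (1 − d) = 0.65, so OR = 1.00 for every d.

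*Case B: deaths strike only patients who would have had an unfavourable outcome anyway.*
- All deaths counted: the rate stays 0.65, OR = 1.00.
- Deaths excluded: OR = 0.35 / (0.35 − d). At d = 5%: 0.35 / 0.30 = 1.17.

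| d (assumed) | Deaths among 315 | A: all counted | A: excluded | B: all counted | B: excluded |
|---|---|---|---|---|---|
| 1% | about 3 | 0.97 | 1.00 | 1.00 | 1.03 |
| 2% | about 6 | 0.95 | 1.00 | 1.00 | 1.06 |
| 3% | about 9 | 0.92 | 1.00 | 1.00 | 1.09 |
| 5% | about 16 | 0.87 | 1.00 | 1.00 | 1.17 |

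Adding a background of non-neurological deaths common to both arms (3% or 5%, also assumed) leaves the Case A result unchanged.

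**Step 4. Is the direction fixed?** At the design rates the OR is (0.76 / 0.24) / (0.65 / 0.35) = 1.705. (Section 12.5 states 1.86 for this pair; that is a separate matter.) Suppose 2.0% of the cilostazol arm and 2.5% of the placebo arm are excluded. The OR becomes (0.76 / 0.22) / (0.65 / 0.325) = 3.455 / 2.000 = 1.727. It rises for cilostazol although placebo had more excluded deaths.

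**The case against.** The strongest defence is that little depends on these analyses. Each exclusion is described as secondary or as a scenario. Section 12.6 treats patients who leave through death as non-responders in the main analysis, and section 4.1.1 puts mRS 3 to 6 in the unfavourable class. Drug-caused deaths also remain visible elsewhere: 28-day mortality is a secondary endpoint, serious adverse events are tabulated in the safety population by treatment received, and a monitoring board reviews them. A fatal intracranial bleed would probably be classed as neurological and keep its mRS 6.

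This stands. A reader might infer from the exclusions that the primary comparison itself loses these deaths; the documents do not support that.

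The defence can also say that the conflict with 12.3 is mild. Section 2.7 reports no difference in major adverse events in earlier trials of 14 days' use, and 10.3.3.2 places the arrhythmia, bleeding and allergy items under research procedures. Listing possible reactions does not predict fatal ones. That explains the optimism in 12.3. It does not justify labelling a whole class of deaths unrelated before cause has been assessed, and sections 2.7 and 4.1.2 attribute these harms to cilostazol explicitly.

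**Conclusion.** The point holds, limited to the secondary and sensitivity analyses and to the missing score. The exclusions can remove drug-caused deaths and no longer compare randomised groups, and the reason given for them conflicts with the protocol's own list of harms. How far they would mislead cannot be known from the documents. The ranges above depend wholly on the assumed 1% to 5% and on which patients die: in one case real harm is hidden, in the other an apparent benefit is created.

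Two stronger readings should be avoided:

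- A reader might infer that exclusion always favours the arm with more non-neurological deaths. On the odds-ratio scale the plan uses, step 4 shows that it need not.
- A reader might infer that the PP estimand scores a non-neurological death from the last recorded mRS, since it falls back on last observation carried forward. The text does not say so. It leaves the value open, and that gap is the defect.

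**What to change.** 1. In 12.2.1 to 12.2.3 and in the 12.3 table, state that every death before 6 months, whatever its cause, is mRS 6 in the ITT and PP estimands.
2. In 12.3, delete the description of these deaths as unrelated to the study and the statement that no drug-related intercurrent event is anticipated.
3. Drop the exclusion scenario from 12.2.1 to 12.2.3, 12.3 and 12.4. If it is kept, label it supplementary and not a robustness check of the primary result, define neurological death, and show it beside a table of cause of death by arm, with cause assigned blind to treatment.

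Narrowing the exclusion to deaths judged unrelated to the drug is not a full remedy, because it still conditions on a post-randomisation event. Assigning cause of death to the adjudication committee would need a wider remit than section 9.3 gives it.

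The cost is an amendment to the wording and, if the scenario is kept, blinded classification of deaths. The sample size does not change. The loss is a neurological-only reading of efficacy, or less weight on it; that reading remains available descriptively.
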